6.12.8.2.2. Analyses of ADA Effects on Efficacy

Efficacy analyses for the Blinded Treatment Dosing Period (Period 2) and Extended Treatment Period (Period 3) will be conducted on all evaluable patients within the ITT Population and Extended Treatment Period Population.

The ASAS40, ASAS20, and ASDAS <2.1 at Week 16 with NRI will be summarized by the TE-ADA status groups as described in Section 6.12.8.2.1.

A logistic regression model with treatment group, TE-ADA status group (excluding patients in the TE-ADA inconclusive category for TE-ADA, excluding TE-ADA positive and co-occurring NAb inconclusive subgroups for NAb) and the interaction of treatment group-by-TE-ADA status group included as factors will be used to test the interaction of treatment group-by-TE-ADA status. The p-value associated with the interaction term will be used to assess if the treatment groups effect is consistent across the TE-ADA status group. When the interaction term is statistically significant, the association between responder status and treatment groups depends, in some manner, on the TE-ADA status group. The interaction will be tested at the 10% significance level. Treatment differences will be evaluated within each subgroup using Fisher's exact test regardless of whether the interaction is statistically significant.

Response rates for ASAS40, ASAS20, and ASDAS <2.1 at Week 16 will be provided and compared among the TE-ADA status (and TE-ADA tiers) and NAb status groups for the ITT Population who were treated with ixekizumab.

Descriptive statistics for ASAS40 and ASAS20 at Week 52 based on the TE-ADA status (and TE-ADA tiers) and NAb status group will be provided for the Extended Treatment Period Population. No inferential statistics will be performed.

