**Statistical Analysis:**

Approximately 300 patients will be randomized at a 1:1:1 ratio in the Blinded Treatment Dosing Period to ixekizumab 80 mg Q2W, ixekizumab 80 mg Q4W, and placebo. With 100 patients per treatment group, this study will have approximately 96% power to test the superiority of ixekizumab Q2W to placebo for the ASAS40 at Week 16. The following assumptions were used for the power calculations for ASAS40 response rates at Week 16 regardless of ixekizumab starting dose: 27% for ixekizumab Q2W treatment group and 7% for placebo group. A 2-sided Fisher's exact test at the 0.05 level is assumed. The efficacy analyses for the Blinded Treatment Dosing Period will be conducted on the intent-to-treat (ITT) population, and safety analyses will be conducted on the safety population.

Comparisons between each ixekizumab treatment group (80 mg Q2W or 80 mg Q4W) and placebo will be performed for all analyses in the Blinded Treatment Dosing Period. Unless otherwise specified, ixekizumab 80 mg Q2W and Q4W groups will be analyzed without regard to starting dose. The primary analysis method for treatment group comparisons of categorical efficacy and health outcomes variables will be a logistic regression analysis with treatment, geographic region, baseline CRP status (nonelevated or elevated), and prior number of TNF inhibitor used (1 or 2) as factors, using the nonresponder imputation (NRI) method. Under NRI, all nonresponders at Week

16 (Visit 8), as well as all patients who discontinue study treatment at any time prior to Week 16 for any reason, will be defined as nonresponders for the NRI analysis at Week 16. Randomized patients without any postbaseline observation will also be defined as nonresponders for the NRI analysis. A graphical multiple testing strategy for the primary and major secondary objectives will be implemented to control the family-wise type I error rate at a 2-sided  $\alpha$  level of 0.05.

The primary analyses for the continuous efficacy and health outcomes variables will be made using mixed-effects model of repeated measures (MMRM) analysis with treatment, geographic region, baseline CRP status, prior number of TNF inhibitor used, baseline value, visit, baseline value-by-visit, and treatment-by-visit as fixed factors.

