
 
• To determine if the effect of either ixekizumab regimen is maintained through Week 52
   
• To explore effect of starting dose (160 mg compared to 80 mg)
   
• To evaluate the incidence of anti-ixekizumab antibodies and their relationship to the efficacy of ixekizumab
   
• To measure ixekizumab exposure and assess the relationship between exposure and efficacy, and exposure and immunogenicity
 
	
All endpoints assessed at Week 16 (above) and during the 16-week placebo-controlled period (above) will continue to be assessed through Week 52 (with the exception of MRI-related endpoints).
 
In addition, the following endpoint is added:
 
 
• NSAID intake (ASAS-NSAID score and % of patients taking NSAIDs)
   
• Onset of action and treatment response (ASAS, ASDAS, CRP, BASFI) during the placebo-controlled period
   
• Efficacy response rates listed below at Weeks 16 and 52 by treatment-emergent anti-drug antibody (TE-ADA) status and by neutralizing anti-drug antibody (NAb) status: 
 
○ Proportion of patients achieving ASAS40
 
○ Proportion of patients achieving ASAS20
 
○ Proportion of patients achieving ASDAS inactive disease
 
 
   
• Serum trough concentrations of ixekizumab
 
• Model parameters for the exposure-response relationship between ixekizumab serum trough concentrations and efficacy endpoints (for example, ASAS20, ASAS40) at Weeks 16 and/or 52
 
• Ixekizumab serum trough concentrations associated with ADA titer sub groups
 

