6.1.1. General Considerations for Analyses during the Blinded Treatment Dosing Period (Period 2)

Comparisons between each ixekizumab regimen (80 mg Q2W or 80 mg Q4W) and placebo will be performed for all analyses in Period 2.

Period 2 starts at the first injection of study treatment at Week 0 (Visit 2) and ends before the first injection of study treatment at Week 16 (Visit 8) or the early termination visit (ETV) (between Weeks 0 and 16).

Baseline will be defined as the last available value before the first injection for efficacy, health outcome, and safety analyses. In most cases, this will be the measure recorded at Week 0 (Visit 2). For efficacy measures, if the patient does not take any injection, the last available value on or before randomization date will be used. Change from baseline will be calculated as the visit value of interest minus the baseline value. For safety analyses using a baseline period, the baseline period is defined as the time from Visit 1 to the date/time of the first injection.

The randomization to treatment groups is stratified by country, screening CRP status (nonelevated versus elevated), and number of prior TNF inhibitors used (1 or 2) as described in Section 5.2. The countries will be categorized into geographic regions for analysis. Geographic regions are defined in Section 6.2. Unless otherwise specified, the statistical analysis models will adjust for geographic region, baseline CRP status, and number of prior TNF inhibitors used.

Unless otherwise specified, treatment groups of ixekizumab 80 mg Q2W and Q4W groups will be analyzed without regard to starting dose.

The primary analysis method for treatment comparisons of categorical efficacy and health outcomes variables at specific time points will be made using a logistic regression analysis with treatment, geographic region (Europe and non-Europe), number of prior TNF inhibitors used, and baseline CRP status in the model using PROC Logistic with a Wald test. The odds ratio and 95% CIs will be reported; treatment difference and 95% CI will also be reported. Secondary analysis will be conducted using a Fisher's exact test. In the case when the logistic regression model does not produce statistical results due to sparse data, Fisher's exact test will be used.

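### The Week 16 treatment-by-TE-ADA tests rest on strata and exclusions that depend on treatment arm, so they cannot show whether the ixekizumab effect is consistent across antibody status

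*SAP*

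**What the plan says.** SAP 6.12.8.2.2 states that the antibody-efficacy analyses "will be conducted on all evaluable patients within the ITT Population and Extended Treatment Period Population". At Week 16 it fits a logistic model with treatment group, TE-ADA status group and their product. TE-ADA-inconclusive patients are left out. For NAb, TE-ADA-positive patients whose NAb result is inconclusive are left out. The stated use is: "The p-value associated with the interaction term will be used to assess if the treatment groups effect is consistent across the TE-ADA status group". The test level is 10%. Fisher tests of treatment difference follow in every subgroup, whatever the interaction shows.

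That paragraph does not name the comparator. SAP 6.1.1 does: "Comparisons between each ixekizumab regimen (80 mg Q2W or 80 mg Q4W) and placebo will be performed for all analyses in Period 2". Table RHBW.6.2 lists each regimen against placebo for the Period 2 ITT Population and has no Q2W versus Q4W comparison. Only the next paragraph of 6.12.8.2.2 is confined to ixekizumab-treated patients; it compares response rates across TE-ADA and NAb groups.

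SAP 6.12.8.1.3 defines TE-ADA positive by a titer rise over baseline, and TE-ADA inconclusive by a drug level that may interfere with the assay. Under Protocol 6.1, placebo patients first receive ixekizumab at Week 16. The objective in Protocol Table RHBW.1 is: "To evaluate the incidence of anti-ixekizumab antibodies and their relationship to the efficacy of ixekizumab".

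**The concern.** The layout copies the baseline-subgroup analysis of SAP 6.13.1: interaction at 10%, then Fisher tests regardless. That layout is sound for a factor fixed before randomisation. TE-ADA is not such a factor. In the ixekizumab arms it marks patients who formed antibody after exposure. In the placebo arm before Week 16 it can mark only assay noise or cross-reactivity. The positive strata of the two arms are therefore different kinds of patient, and so are the negative strata.

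The exclusion adds a second dependence on arm. Barring dosing errors, placebo samples contain no drug before Week 16, so the inconclusive filter can remove ixekizumab patients only.

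At stake is a prespecified p-value with a stated interpretation that it cannot support, together with subgroup treatment effects that could be reported as if randomised.

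**Working it through.** **The plan's own figure.** The Protocol synopsis gives: "With 100 patients per treatment group, this study will have approximately 96% power to test the superiority of ixekizumab Q2W to placebo", with ASAS40 rates of "27% for ixekizumab Q2W treatment group and 7% for placebo group"; a 2-sided Fisher's "exact test at the 0.05 level is assumed". Exact enumeration over two binomials with n = 100 gives 96.5%, so the stated power is reproduced. That power belongs to the full arms, not to antibody strata.

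**Assumed inputs.** The documents give no TE-ADA rate. I take 5 to 15 positives per 100 on each ixekizumab regimen and 0 or 1 on placebo as the base case. I then vary the placebo rate f from 0 to 10% and the ixekizumab rate g from 5 to 20%.

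**Step 1: can the interaction be estimated?** A finite estimate needs at least one responder and one non-responder in all four treatment-by-TE-ADA cells. With 0 placebo positives the cell is empty. With 1 it is 0/1 or 1/1. In neither case does a finite estimate exist.

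For rates rather than fixed counts, with 100 placebo patients:
- Chance of no placebo positive: (1 − f)^100.
- Chance of no TE-ADA-positive placebo responder: (1 − 0.07f)^100.
- Share of 20,000 simulated trials per scenario with a finite estimate (100 versus 100, true rates 27% and 7% in every stratum, no true interaction, no covariates, g from 5 to 20%): last column.

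| f | Expected placebo positives | None positive | No positive responder | Finite estimate |
|---|---|---|---|---|
| 0% | 0 | 100% | 100% | 0% |
| 1% | 1 | 37% | 93% | 3–4% |
| 2% | 2 | 13% | 87% | 8–11% |
| 5% | 5 | 0.6% | 70% | 22–29% |
| 10% | 10 | <0.1% | 49.5% | 37–50% |

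The 6.1.1 fallback for sparse data, Fisher's exact test, does not test an interaction. NAb status is grouped only among TE-ADA positives (SAP 6.12.8.2), so its cells are smaller still.

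**Step 2: Fisher test in the positive subgroup.** With n ixekizumab positives and 1 placebo positive, the most extreme table has p = 1/(n + 1):
- n = 5: 1/6 = 0.167
- n = 10: 1/11 = 0.091
- n = 15: 1/16 = 0.062

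None can fall below 0.05. With more placebo positives, power for 27% versus 7% (5 to 20 ixekizumab positives) is at most 0.2% with 1 or 2, 0.6 to 2.0% with 5, and 5 to 8% with 10.

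**Step 3: does the estimate mean what the SAP says when it exists?** Suppose the true benefit is 20 points for everyone, 10% of patients would form antibody, and those patients respond at 2% on placebo. The others then respond at (7 − 0.1 × 2)/0.9 = 7.56% on placebo. If placebo positives are assay noise, placebo shows 7% in both strata.
- TE-ADA-positive difference: (2 + 20) − 7 = 15.0 points.
- TE-ADA-negative difference: (7.56 + 20) − 7 = 20.6 points.

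An apparent interaction of 5.6 points appears where none exists. Its sign comes from the assumed prognosis of antibody formers.

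**Step 4: direction in the negative subgroup.** Take 27 responders per 100 on ixekizumab, 10 positives, and r responders among them. The negatives respond at (27 − r)/90. For r = 1 this is 26/90 = 28.9%. For r = 3 it is 24/90 = 26.7%. The shift changes sign between r = 2 (25/90 = 27.8%) and r = 3, and the documents do not say what r would be.

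**The case against.** **Placebo inclusion is inferred.** The model paragraph never names placebo. That stands. The inference is strong, however: 6.1.1 and Table RHBW.6.2 set the Period 2 comparison, and the next paragraph's limit to ixekizumab-treated patients would be redundant if placebo were already out. If ixekizumab-only was intended, the text still has to say so.

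**The objective is already served.** The ixekizumab-only comparison is planned, and Protocol Table RHBW.1 asks only for response rates by TE-ADA and NAb status. That stands too. It means the contested tests can go without loss.

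**Little harm is likely.** This is an other-secondary analysis without multiplicity adjustment. In the no-interaction simulations, rejection over all trials was at most 5.7% against a nominal 10%. The likelier result is an uninformative table than a false finding. That limits the weight of the point but does not make the stated interpretation valid.

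**A stronger reading.** A reader might infer that the TE-ADA-negative effect will look inflated because poorer responders leave the ixekizumab arms. The documents do not support a direction. Nothing in them says that antibody-positive patients respond worse. A mechanism within the plan also points the other way: early discontinuers count as failures (SAP 6.3.1 and 6.10.1) and give fewer Period 2 samples in which to turn positive, which adds failures to the negative group.

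**Conclusion.** Wrong as written. That strata and exclusion depend on arm follows from the SAP's own definitions and needs no assumed rate. The interaction p-value cannot show whether the treatment effect is consistent across TE-ADA status.

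The size of the sparse-cell problem does rest on assumption. With 0 or 1 placebo positives there is no finite interaction estimate, and with 5 to 15 ixekizumab positives the positive-subgroup Fisher test cannot reach p < 0.05. Even at a 10% placebo rate, about half or more of simulated trials gave no finite estimate. The simulation used one ixekizumab group against placebo.

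A reader might also infer that the trial's efficacy conclusions, or the antibody objective as a whole, are compromised. Neither follows. The primary and major secondary analyses do not use TE-ADA, and a suitable comparison for the objective is already in the SAP.

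**What to change.** In SAP 6.12.8.2.2:
- Delete the treatment-by-TE-ADA and treatment-by-NAb interaction tests and the ixekizumab versus placebo Fisher tests within those subgroups.
- Keep the ixekizumab-only comparison of response by TE-ADA and NAb status as the analysis for this objective, labelled as a non-randomised association.
- Show inconclusive patients as their own category.
- Use description only where cells are small, for example by carrying over the <10% rule of 6.13.1. With about 200 ixekizumab patients that means groups under 20; rates of 5%, 10% and 15% would give 10, 20 and 30 positives.
- Report placebo TE-ADA as assay background only.

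Do not substitute a regimen-by-TE-ADA interaction model. Q2W versus Q4W is also a randomised contrast and TE-ADA may depend on regimen, so the same fault returns. It would also be sparse. If positives respond at 10% (assumed) and each arm has m of them, the chance that at least one arm has no positive responder is 1 − (1 − 0.9^m)^2: 83%, 58% and 37% for m = 5, 10 and 15.

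The cost is SAP wording and fewer outputs. SAP Version 4 postdates the first unblinding (SAP 3), so if the Week 16 tables already exist, the study report should record the change and not interpret the interaction p-value.

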6.12.8.2.3. Analyses of Treatment-Emergent ADA Effects on Specific Adverse Events

The analyses of TE-ADA effects on safety will be conducted on all evaluable patients within the defined Safety Population for Blinded Treatment Dosing Period (Period 2) and Combined Blinded Treatment Dosing and Extended Treatment Periods (Combined Periods 2 and 3).

Baseline definition for immunogenicity analyses for the Combined Treatment Period is the same as [Table RHBW.6.10](#).

Adverse events of special interest (AESI) of allergic reaction/hypersensitivity (anaphylaxis and nonanaphylaxis) and of injection-site reactions will be included in an assessment of AE to TE-ADA over time. Timing of an AE will be taken to be the reported AE start date.

For each TE-ADA status dichotomous variable (as defined in [Table RHBW.6.11](#)), patients will be categorized according to whether they were (i) always in lesser-TE-ADA status postbaseline or (ii) at some point postbaseline, were in greater-TE-ADA status. For each AESI, within the time-varying TE-ADA status groups, a summary will be provided of the number of patients who had no event, events only while in lesser-TE-ADA status for group (i), or for group (ii) – at least 1 event while in greater-TE-ADA status.

Additionally, summaries will be provided of the total number of AESI events (with unique start dates) by time-varying TE-ADA status groups at the event date. The summaries will aggregate time respectively in greater-TE-ADA status and in lesser-TE-ADA status, along with the event rates (rates per 100 patient-years) relative to those aggregate times.

By-patient listings will be provided of patients with TE-ADA who experience a treatment-emergent allergic reaction/hypersensitivity reaction or an injection-site reaction.

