**Observation:** Patients are to remain under observation for at least 1 hour after dosing at Week 0 (Visit 2) and Week 16 (Visit 8) to monitor for safety, since some patients will be receiving ixekizumab for the first time at these visits. Therefore, at Week 16 (Visit 8), injections of the investigational product will be administered by the patient or caregiver at the clinical site to allow for observation for any AEs and collection of post-injection blood pressure (BP) and pulse measurements approximately 1 hour after administration of the investigational product (Section 8.4.2 and Appendix 2).

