6.12.8.1.3. Definitions for Clinical Interpretation of Assay Results

- Baseline:** For immunogenicity analyses during Period 2, baseline is the last nonmissing observation on, or before, the date of the first injection of study treatment (Week 0). Unless otherwise specified, the baseline for subsequent treatment periods is defined as the last nonmissing observation on, or before, the date of first injection of ixekizumab. For patients originally randomized to ixekizumab during Period 2, baseline is the last nonmissing observation on, or before, the date of the first injection of study treatment for Period 2 (Week 0). For patients who are not originally randomized to ixekizumab in Period 2, baseline is the last nonmissing observation on, or before, the date of the first injection of ixekizumab. See [Table RHBW.6.10](#) for further details.

[figure not shown]
Table RHBW.6.10. Baseline Definition for Immunogenicity Analyses for Extended Treatment Period

Treatment Assignment for Blinded Treatment Dosing Period (Period 2)	Treatment Assignment for Extended Treatment Period (Period 3)	Baseline for Extended Period Analysis ^a
Ixekizumab	Ixekizumab	Week 0
Placebo	Ixekizumab	Week 16

^a Last nonmissing observation on, or before, the date of the first injection of study treatment at the defined week.

- **Baseline ADA positive (pre-existing antibody):** ADA detected in a sample collected at baseline
- **Treatment-emergent antidrug antibody (TE-ADA) positive:** a) a patient with a ≥ 4 -fold increase over a positive baseline antibody titer (Tier 3); or b) for a negative baseline titer, a patient with an increase from the baseline to a level of $\geq 1:10$
- **Baseline ADA-negative:** ADA is not detected in a sample collected at baseline.
- **TE-ADA inconclusive patient:** A patient without a TE-ADA positive sample and with at least 1 sample for which drug levels may interfere with the ADA assay
- **TE-ADA negative patient:** A patient who is evaluable for TE-ADA and is not either TE-ADA positive or TE-ADA inconclusive

Figure RHBW.6.6 illustrates the relationship of some of these terms.

Abbreviation: ADA = anti-drug antibody.

[figure not shown]
Figure RHBW.6.6. Relationship of terms for clinical interpretation of assay results for evaluable patients.

- **Incidence of TE-ADA:** Patients with TE-ADA as a proportion of the evaluable patient population during the treatment period. This excludes unevaluable patients.

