For each TE-ADA status dichotomous variable, a time-varying TE-ADA status will be computed. At time t the TE-ADA status is taken to be the highest of the TE-ADA values bracketing time t . More formally, the TE-ADA status at time t is given by the greater of (a) the TE-ADA status at the most-recent postbaseline measurement before t , and (b) the TE-ADA status at the first TE-ADA postbaseline measurement at or after time t . In this computation, “greater” is given by the greater-TE-ADA status of [Table RHBW.6.11](#). If there is no value satisfying criterion (a), then the value (b) is used. Similarly, if there is no value (b), then the value (a) is used.

For each TE-ADA status dichotomous variable, patients will be categorized according to whether they were (i) always in lesser-TE-ADA status postbaseline or (ii) at some point postbaseline, were in greater-TE-ADA status.

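### Reaction rates by TE-ADA status are not stratified by time since first ixekizumab dose, so the contrast is confounded if reaction risk changes with time on drug

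*SAP*

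**What the plan says.** SAP 6.12.8.2.3 covers two groups of events: allergic reaction/hypersensitivity (anaphylaxis and non-anaphylaxis) and injection-site reactions. It is run for Period 2 and for Combined Periods 2 and 3. Events are assigned to the antibody status held on their start date: "summaries will be provided of the total number of AESI events (with unique start dates) by time-varying TE-ADA status groups at the event date". The denominators follow: "The summaries will aggregate time respectively in greater-TE-ADA status and in lesser-TE-ADA status, along with the event rates", per 100 patient-years. This is done for each of the three dichotomous variables in SAP Table RHBW.6.11 (any positive, moderate-to-high titer, high titer).

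SAP 6.12.8.2 defines the status: "At time t the TE-ADA status is taken to be the highest of the TE-ADA values bracketing time t". Before the first postbaseline sample, "If there is no value satisfying criterion (a), then the value (b) is used". Positivity is therefore back-dated to the preceding sample, or to the first dose if the Week 1 sample is positive. It can also revert once later samples are not positive.

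For a patient negative at baseline, SAP 6.12.8.1.3 defines TE-ADA as "a patient with an increase from the baseline to a level of" 1:10 or more. Samples are scheduled at Weeks 0, 1, 2, 4, 8, 12 and 16, then 24, 28, 36 and 52 (Protocol Appendix 2).

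No test, rate ratio or confidence interval is specified for these rates. Protocol 9.7.3 nevertheless describes the purpose as a comparison by antibody status.

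**The concern.** The question is whether antibodies change the reaction rate. TE-ADA is a change after dosing starts, and SAP 6.12.8.2.1 itself plans time-to-development summaries with Kaplan-Meier plots. Time spent positive and time spent not positive may therefore sit at different points on the time-on-drug scale. If reaction risk also varies along that scale, time on drug confounds the contrast.

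There is some reason to expect that it varies. Every patient has 2 injections at Week 0 and 1 every 2 weeks afterwards. Protocol 6.1.1 also requires at least an hour of observation after the Week 0 and Week 16 doses, "to monitor for safety, since some patients will be receiving ixekizumab for the first time at these visits". That shows concern about first exposure; it is not evidence that reactions cluster there.

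At stake is the planned rate-based look at whether anti-ixekizumab antibodies carry a safety cost. Two adjacent rates invite a direct reading, and that reading could be wrong in either direction.

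**Working it through.** The plan states no figure for this analysis, so there is nothing to reproduce. The check asks what the crude ratio would be if antibodies had no effect at all.

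**Inputs from the documents.** The sampling weeks and status rule given above. Injections in Period 2 (SAP 6.8): 9 in total, with 2 at Week 0 and 1 every 2 weeks from Week 2 to Week 14. That is 3 in the first 4 weeks and 6 in the next 12, or 2 per 4 weeks, so the early excess in injection count is 3/2 = 1.5.

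**Assumptions, because the documents give no values.** The reaction rate in Weeks 0 to 4 is k times the later rate, with k = 1, 1.5, 2, 5 or 10. Either 5% or 20% of patients are ever positive. Several onset and persistence patterns are tried. Only ixekizumab time is counted.

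**Formula.** Let p be the share of greater-status time that falls in Weeks 0 to 4, and q the same share of lesser-status time. With no antibody effect,

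crude ratio = [1 + (k − 1)p] / [1 + (k − 1)q].

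**Period 2, onset uniform over Weeks 0 to 16, persistent.** By sampling interval, the onset probabilities are 1/16, 1/16, 2/16, 4/16, 4/16 and 4/16. After back-dating, status starts at Week 0, 1, 2, 4, 8 and 12.
- Mean greater-status time per positive patient: (16 + 15 + 28 + 48 + 32 + 16)/16 = 155/16 = 9.69 weeks.
- Part of it in Weeks 0 to 4: (4 + 3 + 4)/16 = 11/16 = 0.69 weeks, so p = 11/155 = 0.071.
- With 5% ever positive, q = (4 − 0.05 × 0.6875)/(16 − 0.05 × 9.6875) = 3.966/15.516 = 0.256.
- With 20% ever positive, q = 3.8625/14.0625 = 0.275.

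| k | 5% ever positive | 20% ever positive |
|---|---|---|
| 1 | 1.00 | 1.00 |
| 1.5 | 1.035/1.128 = 0.92 | 1.035/1.137 = 0.91 |
| 2 | 1.071/1.256 = 0.85 | 1.071/1.275 = 0.84 |
| 5 | 1.284/2.022 = 0.63 | 1.284/2.099 = 0.61 |
| 10 | 1.639/3.300 = 0.50 | 1.639/3.472 = 0.47 |

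At k = 10 and 5% ever positive, a true doubling throughout greater-status time would show as about 2 × 0.50 = 1.0.

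**Other patterns, 5% ever positive, k = 2 / 5 / 10.**

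| Pattern | p | q | Crude ratio |
|---|---|---|---|
| 0–52 weeks, onset over 0–16, persistent | 0.015 | 0.080 | 0.94 / 0.80 / 0.66 |
| 0–52 weeks, onset over 0–52, persistent | 0.007 | 0.079 | 0.93 / 0.78 / 0.62 |
| 0–52 weeks, onset over 0–16, lasting 8 weeks | 0.054 | 0.077 | 0.98 / 0.93 / 0.88 |
| Period 2, onset by Week 1, persistent | 0.250 | 0.250 | 1.00 / 1.00 / 1.00 |
| Period 2, onset by Week 1, lasting 4 weeks | 0.500 | 0.244 | 1.21 / 1.52 / 1.72 |
| 0–52 weeks, onset by Week 1, lasting 4 weeks | 0.500 | 0.074 | 1.40 / 2.32 / 3.31 |

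With 20% ever positive, the last two rows reach 1.83 and 3.50 at k = 10.

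**After stratifying.** A Mantel-Haenszel ratio across bands of weeks on drug is 1.00 in every pattern. It is exact here because the assumed rate is constant within bands; with real data some residual confounding within windows would remain.

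**The case against.** A reader might infer that positive time is later on drug by design, so that antibodies are bound to look harmless. The documents do not support that. The SAP back-dates positivity, to the first dose if Week 1 is positive. Status can revert, and lesser-status time includes the late follow-up of patients who never convert. In the 8-week transient pattern over 52 weeks, positive time is earlier on average (13.1 versus 26.2 weeks). Later positive time is a tendency that depends on unknown onset and persistence, and early transient antibodies reverse the bias.

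Early clustering of reactions is likewise an assumption. The observation rule is a precaution. The double injection at Week 16 keeps the blind and falls late on drug for patients randomized to ixekizumab. Only the Week 0 double injection gives a documented early excess, and its effect is small (about 0.92).

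A reader might also think of lost power or false-positive findings. The SAP plans no test on these rates, so there is no planned decision to which such figures would apply.

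Other features can raise the ratio. Protocol 8.4.9 adds an antibody sample after a suspected systemic reaction, and SAP 6.12.8.2.1 includes unscheduled samples; under the highest-value rule such a sample can move the event into positive time. SAP 6.12.8.2.3 does not say the rates are by arm. If placebo supplied one third of lesser-status time at 0.3 of the ixekizumab rate (assumed), the ratio would rise by 1/(2/3 + 0.3/3) = 1.30.

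Finally, the rates are descriptive and sit beside a patient-level summary and listings, and SAP 6.12.3.1 lets a program safety analysis plan, not available here, supersede special-topic analyses. None of these outputs, as visible, controls time on drug. The Period 2 versus combined split does not either, and in the gradual, persistent patterns the distortion is larger in Period 2. These objections limit the claim about direction and size; the omission stands.

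**Conclusion.** The point holds in a limited form. The visible SAP plans crude reaction rates by TE-ADA status with no control for time since first ixekizumab dose. If risk changes with time on drug, the contrast is confounded.

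With gradual, persistent antibodies and early reactions, the Period 2 ratio is pulled to roughly 0.8 to 0.5 for a 2- to 10-fold early excess, and to about 0.9 at 1.5-fold. With early, short-lived antibodies it rises above 1. With no early excess it is unbiased. Neither the direction nor the size can be fixed from the documents, because they give no data on when reactions or antibodies occur.

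This is a supporting safety display and does not touch the efficacy conclusions. The change is worth making because it removes this confounding in either direction with data already collected.

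**What to change.** In SAP 6.12.8.2.3, report events, patient-years and rates by time-varying TE-ADA status within windows of time since the first ixekizumab injection, for example Weeks 0–4, >4–16 and >16–52. Timing from first ixekizumab rather than from randomization places placebo patients who switch at Week 16 correctly. Restrict the analysis to ixekizumab-exposed time, or include arm as a factor. Add a window-stratified rate ratio (Mantel-Haenszel or Poisson) with a 95% CI where events suffice, and keep the crude rates as a supporting display.

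The cost is a sentence or two in the SAP and one more stratification variable in tables already planned, with no new data. The downside is sparse cells, especially for anaphylaxis and for the high-titer variable; there the windowed counts can stand without a ratio. Stratification does not deal with samples triggered by a reaction, which would need a separate sensitivity analysis.
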